1 INTRODUCTION

This Statistical Analysis Plan codifies the analysis of a retrospective research study that has been previously reviewed and approved (2017P002261) by the Partners HealthCare Institutional Review Board (IRB) and will be conducted in accordance with all applicable human subjects' research requirements and applicable federal regulations.

1.1 Study Introduction

Briefly, this study examines the occurrence and neurological consequences of atrial fibrillation, occurring after discharge to home or rehab after cardiac surgery. The study examines patients who underwent cardiac surgery at Cardiac Surgical Programs in Massachusetts between 1/1/2012 and 12/31/2016, with a follow-up period that extends to 12/31/2017.

Detailed data will be obtained from individual Programs that encompasses preoperative medical history, the operative period including details about the operation and also the post-operative period until discharge from hospital. Information about the post-hospital discharge course for individual patients will be obtained from the Massachusetts Center for Health Information and Analysis (CHIA) (<https://www.mass.gov/orgs/center-for-health-information-and-analysis>). CHIA collects detailed financial and patient-level data from Massachusetts payers and providers, and makes it available to researchers.

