2 STUDY SUMMARY AND AIMS

The purpose of this study is to determine the incidence, risk factors and adverse events consequent upon atrial fibrillation after cardiac surgery, as well as the association between prior atrial fibrillation and postoperative atrial fibrillation. The study uses information from local Cardiac Surgical Programs to describe the preoperative medical state and immediate post-operative state. Additionally, information from the post-discharge period will be provided by CHIA, by matching the two sources of information using HIPAA-waived data such as medical record number, date of birth, gender and last name. Once matched, the data are stripped of identifiers.

2.1 Study Design:

We will employ a retrospective cohort design, examining patients who underwent cardiac surgery at Cardiac Surgical Programs in Massachusetts between 1/1/2012 and 12/31/2016, with a follow-up period that extends to 12/31/2017. The study examines the risk factors and incidence of post-operative atrial fibrillation, stroke and other focal neurological events after discharge from hospital.

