2.2 Study Population and Sites

The study will examine the medical records of patients who underwent cardiac surgery in Massachusetts between 1/1/2012 to 12/31/2016. It is estimated that ~50,000 patients are eligible for inclusion in this study. The evaluable sample size is derived from a sample of convenience from the following Institutions.

Baystate Medical Center, Springfield, MA
Beth Israel Deaconess Medical Center, Boston, MA
Brigham and Women's Hospital, Boston, MA
Cape Cod Hospital, Hyannis, MA
SouthCoast Health, Fall River, MA
Massachusetts General Hospital, Boston, MA
Mount Auburn Hospital, Cambridge, MA
UMass Memorial Medical Center-University, Worcester, MA

Tufts Medical Center, Boston, MA

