5 DATA SOURCES

6 STUDY POPULATIONS

6.1 Inclusion Criteria

Inclusion criteria for this study are patients who undergo surgical procedures that include coronary artery bypass graft surgery, aortic valve surgery or mitral valve surgery and other valvular surgical procedures.

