7.1.1 Primary Aims

The standard Cox proportional hazards model will be used to model time to first atrial fibrillation occurrence and time to first stroke or other focal neurologic event, after discharge from hospital,

respectively. The potential risk factors included will be selected based on their univariate association with first event status, as well as clinical significance. Hazard ratios with 95% confidence intervals will be reported with a two-sided p-value for statistical significance. The proportional hazard assumption will be evaluated using graphical tool, and by including time dependent covariate terms.

Since there might be repeated occurrences of atrial fibrillation and stroke or other focal neurologic event for each patient, we will use the Andersen-Gill (AG) model and the Prentice, Williams and Peterson (PWP) models to analyze recurrent events data. The AG model is suitable when the interest is in the overall effect on the intensity of the occurrence of a recurrent event. The PWP models allow us to evaluate the effects of risk factors for the kth event after discharge from hospital, as well as the effects of risk factors for the kth event since the time from the previous event (47). Hazard ratios with 95% confidence intervals will be reported with a two-sided p-value for statistical significance. For time-to-event data analyses, death will be considered a censoring event.

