10 APPENDIX: CHIA-SOURCED VARIABLE DEFINITIONS AND ABSTRACTION

We will create a subset of cardiac surgery patients using all three CHIA databases to maximize the chance of finding a matching cardiac surgery record in RPDR. UHINs for the cardiac surgery cases are identified in the inpatient database where at least one of 15 procedure codes or principal procedure contains an ICD9-CM code for cardiac surgery (3610-3619). The following lists the minimum set of fields needed to complete the merge.

- a. MDPHHospNum: MDPH hospital number determined from all hospital IDs in the case mix data
- b. AdmitDt: Admission date to hospital
- c. ProcDates: Possible dates for cardiac surgical procedure (15 in inpatient, 3 in OOR data)
- d. ProcedureCodes: ICD-9-CM and CPT (OOR only) codes for cardiac surgery records (only 3 ICD-9-CM in OOR data)
- e. PrincipalProcDate: Date for principal procedure (OOR only)
- f. PrincipalProcedure: ICD9-CM code for PCI and CABG records
- g. Diagnosis Codes: Diagnosis and DRG codes for conditions
- h. DischDate: Discharge date from hospital
- i. RecordType20ID: CHIA Record Id Control Number
- j. UHIN Unique patient identifier from CHIA
- k. DOB: Patient date of birth submitted by hospital
- l. MedicalRecordNum: Hospital patient medical record number
- m. Gender: Patient gender

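### Post-discharge AF and stroke are ascertained only through Massachusetts data, but eligibility ignores residence and no rule handles patients who cannot be observed there

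*Combined protocol and SAP*

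**What the plan says.** **Who is in.** Section 2.2 takes "patients who underwent cardiac surgery in Massachusetts between 1/1/2012 to 12/31/2016". Section 6.1 includes "patients who undergo surgical procedures that include coronary artery bypass graft surgery", together with valve procedures. The exclusions in Section 6.2 concern earlier AF procedures and the type of operation. None concerns where the patient lives or will receive later care.

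**Where outcomes come from.** Section 2 states that "information from the post-discharge period will be provided by CHIA", and Section 1.1 gives that source's reach: "CHIA collects detailed financial and patient-level data from Massachusetts payers and providers". The Table 1 shell in Section 12 lists CHIA as the only source for every post-discharge AF and stroke interval. It lists 30-day, 1-year and 5-year mortality as Program-sourced.

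**How patients are linked.** Section 10 says "UHINs for the cardiac surgery cases are identified in the inpatient database", so a patient enters through the in-state surgical admission.

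**How follow-up ends.** The study closes on 12/31/2017. The only censoring event named is in Section 7.1.1: "For time-to-event data analyses, death will be considered a censoring event". The Poisson models in Section 7.1.2 use follow-up length as the offset, and nothing limits it to time observable in CHIA.

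**Residence.** ZIP code is line 5 of the Program data request in Section 9. No analysis uses it.

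**The concern.** A non-resident operated on in Massachusetts has an index admission in CHIA and can be matched. If that patient goes home and is treated there for AF or stroke, the event need not appear in CHIA. The plan gives no instruction for this case, so the patient stays in the risk set without an event and the person-time enters the denominator.

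Two sets of aims are exposed. Secondary Aims 1 and 2 include the frequencies of post-discharge AF and stroke, which missed events lower directly. The Primary Aims concern risk factors, with prior AF as the main one. Those associations are distorted if the non-resident share differs by risk-factor level. A large sample does not protect against this.

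The plan's other safeguards do not address the gap:

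- The missing-outcome exclusion in Section 7.3 does not say that absence of a CHIA record counts as missing.
- The negative-control and E-value analyses (Sections 3.4 and 7.6) are aimed at unmeasured confounding, not incomplete capture. A fracture outcome from the same source would be missed in the same patients.
- The STROBE checklist in Section 13 asks, at item 12(d), how loss to follow-up was addressed. The plan has no text on it.

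**Working it through.** **1. The plan's own figure (Section 4).** Inputs: 50,000 patients, 4,000 (8%) with prior AF, two-sided 0.05, 80% power, 25% AF without prior AF.

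Detectable h = (1.960 + 0.842) × √(1/4,000 + 1/46,000) = 0.0462. An h of 0.046 from 25% gives 27.0%. The stated 0.046 and 2-point difference are reproduced. The sample-size figure is not at fault, and 25% versus 27% is used below as the reference case.

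**2. Effect on frequency.** Let f be the non-resident share and c the fraction of their events that CHIA still captures. Both are assumptions; the documents give neither.

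Observed incidence = 25% × (1 − f(1 − c))

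| f | c = 0 | c = 0.5 |
|---|---|---|
| 5% | 23.8% | 24.4% |
| 10% | 22.5% | 23.8% |
| 15% | 21.3% | 23.1% |

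The same factor applies to stroke frequency.

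**3. Effect on the prior-AF association, c = 0.** Let f1 be the non-resident share with prior AF and f0 the share without.

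Observed risk ratio = [27% × (1 − f1)] / [25% × (1 − f0)]; the true value is 27/25 = 1.08.

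| f1 | f0 | Prior AF | No prior AF | Difference (points) | Risk ratio |
|---|---|---|---|---|---|
| 10% | 10% | 24.30% | 22.50% | 1.80 | 1.08 |
| 15% | 10% | 22.95% | 22.50% | 0.45 | 1.02 |
| 5% | 10% | 25.65% | 22.50% | 3.15 | 1.14 |

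With no true difference (25% in both groups), a 5-point gap in f creates a false difference of 25% × 5 points = 1.25 points, against a detectable difference of 2 points. These are crude two-group risk ratios. They indicate the direction and rough size of the effect on a hazard ratio, not the value an adjusted Cox model would return.

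**4. Cost of restricting to residents.** The prior-AF share is held at 8%.

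| f | N | Detectable h | Detectable difference (points) | Power, 25% vs 27% |
|---|---|---|---|---|
| 0 | 50,000 | 0.0462 | 2.0 | 79.4% |
| 5% | 47,500 | 0.0474 | 2.1 | 77.3% |
| 10% | 45,000 | 0.0487 | 2.1 | 75.1% |
| 15% | 42,500 | 0.0501 | 2.2 | 72.7% |

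Keeping 10% non-residents with no capture gives 73.7% power, because the observed difference shrinks to 1.8 points. At that share, restriction does not lose power relative to the plan as written, and it removes the understatement due to non-residents.

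**The case against.** **Nothing says these patients are counted as event-free.** A reader might infer that the plan instructs this. It does not. Section 7.3 excludes patients with missing outcomes, and Figure 1 has a box for them. But no text classes a patient with no later CHIA record as missing, so event-free follow-up is the default consequence of the rules as written.

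**Not all their events are lost.** A reader might infer that every later event in a non-resident is missed. The source covers payers as well as providers, so a non-resident who returns to a Massachusetts hospital, or perhaps has a Massachusetts payer, may be captured. This stands, and the c = 0 column is an upper bound for a given share. Section 9 also requests a 30-day readmission field and reason. It is not listed for STS 2.81, and the plan does not name it as a source for AF or stroke.

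**The hazard ratios may be sound.** A reader might infer, for instance from referral of complex cases to large centers, that the prior-AF association is attenuated. The documents give no residence split by prior AF. Equal shares leave the ratio about unchanged, and unequal shares can move it either way. Section 7.2 makes site a random effect in the logistic and Cox models, and Section 7.4.1 specifies covariate adjustment. These could absorb part of a capture difference between sites. They do not correct differences within a site, and they do not restore the frequencies.

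**Mortality is a different matter.** It is Program-sourced in Table 1, so the CHIA argument does not extend to it. This stands and limits the point to AF and stroke.

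**Conclusion.** The point holds for post-discharge AF and stroke. Eligibility follows the place of surgery, ascertainment follows Massachusetts payers and providers, and no rule connects the two. Followed as written, the plan understates AF and stroke frequency to the extent that non-residents receive later care elsewhere. Under assumed shares of 5% to 15%, that is about 1.3 to 3.8 points off a true 25% with no capture, and about half that if half their events are captured.

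For the prior-AF association, the documents support only a conditional statement: no material change if non-residence is unrelated to prior AF, and bias of unknown direction otherwise. A 5-point gap in either direction moves a risk ratio of 1.08 to about 1.02 or 1.14. The actual non-resident share, its split by prior AF and the degree of capture are unknown, so no single bias figure should be quoted.

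**What to change.** Amend Section 6.1 so that the post-discharge AF and stroke analyses include only patients who were Massachusetts residents at surgery, determined by ZIP code. Keep all eligible patients in the mortality analyses. Repeat the AF and stroke analyses in all patients as a sensitivity analysis under Section 7.6. Show the number removed, by prior-AF status, in Figure 1; this also tells the reader whether the ratio could have been affected.

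ZIP code is already requested, but this is a data-flow step as well as an eligibility line. Section 2 removes identifiers after matching, and Section 8.1 says the final analytic file holds no addresses. The residence flag must therefore be derived before that step and carried forward as a yes/no variable.

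The cost is a somewhat smaller sample (at 10% non-residents, N = 45,000 and a detectable difference of about 2.1 points) and results that apply to state residents. Residence at surgery does not identify residents who later move or seek care elsewhere. That loss remains and should be acknowledged as a limitation.

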1.2 Background Literature

Atrial fibrillation (AF) is the most common cardiac arrhythmia and frequently presents in association with mitral, other valvular and coronary artery disease, notably in the presence of poorer left ventricular function (1,2). Preoperative AF is reported commonly in patients undergoing cardiac surgery, with an incidence of 10-20% (2-8). Even if treated, preoperative AF is associated with a higher incidence of in-hospital postoperative AF, stroke, other cardiac morbidity and mortality (2,6,9-11).

Conventional management of postoperative AF assumes that it results from self-limited causes, such as postoperative pericarditis, surgical stress, and sympathetic stimulation in patients underlying heart disease that can be treated with short-term antiarrhythmics, heart rate reduction, anti-coagulants and anti-platelet agents. However, it is well-known that AF in the immediate postoperative period is associated with increased risk of post-discharge AF and stroke. Observed incidences range widely (3-25%) depending principally on the duration of follow-up and the mode of monitoring (12-14). These studies did not use continuous ECG monitoring to detect AF recurrence, and therefore may have underestimated the incidence of AF by missing asymptomatic AF. Using continuous ECG monitoring the incidence of at least one electrocardiographic episode of AF lasting longer than six minutes is much higher; 60% over the entire follow-up period and 39% occurring more than 3-months after surgery (15).

Thromboembolic stroke is a major preventable cause of morbidity and mortality in patients with post-operative AF (16-18). Studies have demonstrated a risk-unadjusted two to ten-fold increase in embolic events and a threefold increased risk of cardiac death in patients with postoperative AF (12,19,20).

The efficacy of concomitant AF ablation in patients undergoing cardiac surgery, measured as freedom from AF and quality of life, and safety measured as freedom from morbidity and mortality, has been well demonstrated (21-29), especially after mitral valve surgery. Observational studies with large sample sizes and longer follow-up have demonstrated improved survival after surgical ablation in normal sinus rhythm (30-33). Yet the implementation of AF ablation and stroke reduction procedures, while increasing (34,35), remains relatively low in the US (33). This is despite guidelines from National and International Societies (36-39) that support use of these procedures. Concerns voiced about concomitant AF ablation or stroke reduction surgery include increased operative time and complexity, perceived operative risk of the procedures (40), and increased risk of atrio-ventricular block requiring pacemaker insertion (21,34,35,41,42).

2 STUDY SUMMARY AND AIMS

The purpose of this study is to determine the incidence, risk factors and adverse events consequent upon atrial fibrillation after cardiac surgery, as well as the association between prior atrial fibrillation and postoperative atrial fibrillation. The study uses information from local Cardiac Surgical Programs to describe the preoperative medical state and immediate post-operative state. Additionally, information from the post-discharge period will be provided by CHIA, by matching the two sources of information using HIPAA-waived data such as medical record number, date of birth, gender and last name. Once matched, the data are stripped of identifiers.

2.1 Study Design:

We will employ a retrospective cohort design, examining patients who underwent cardiac surgery at Cardiac Surgical Programs in Massachusetts between 1/1/2012 and 12/31/2016, with a follow-up period that extends to 12/31/2017. The study examines the risk factors and incidence of post-operative atrial fibrillation, stroke and other focal neurological events after discharge from hospital.

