2.3 Primary Aims

The Primary Aims of this study are to determine:

1. The risk factors, which includes the main risk factor preoperative atrial fibrillation, for postoperative atrial fibrillation occurring after discharge from hospital in patients who underwent cardiac surgery during admission.
2. The risk factors, which includes the main risk factor preoperative atrial fibrillation, for stroke or other focal neurologic event occurring after discharge from hospital in patients who underwent cardiac surgery during admission.

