2.4 Secondary Aims

The Secondary Aims of this study are to determine:

1. The frequency of, and treatments for, atrial fibrillation occurring after discharge from hospital in patients who underwent cardiac surgery during admission.
2. The frequency of stroke or other focal neurologic event occurring after discharge from hospital in patients who underwent cardiac surgery during admission
3. The incidence of all-cause and stroke-related mortality after cardiac surgery.

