7.1.2 Secondary Aims

Means and standard deviations will be estimated for count outcomes. We will report the two-sided p-value for statistical significance of the difference in means of count outcomes.

The frequencies of atrial fibrillation and stroke or other focal neurologic event will be modeled with Poisson regression with the length of follow-up time as the offset. Potential risk factors included in this model will be selected based on univariate test results, as well as clinical significance. Logistic regression will be used to model the incidence of all-cause and stroke-related mortality after cardiac surgery, respectively.

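### The consequences of post-discharge AF are part of the stated purpose, but no aim or adjusted model uses post-discharge AF as an exposure, and Figures 3 and 4 compare by it without a time rule

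*Combined protocol and SAP*

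**What the plan says.** Two introductory statements make the consequences of AF part of the study. Section 1.1: "this study examines the occurrence and neurological consequences of atrial fibrillation, occurring after discharge to home or rehab after cardiac surgery". Section 2: the purpose is to "determine the incidence, risk factors and adverse events consequent upon atrial fibrillation after cardiac surgery", together with the association between prior and postoperative AF.

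The aims take a different exposure. Primary Aim 2 in Section 2.3 is "The risk factors, which includes the main risk factor preoperative atrial fibrillation, for stroke or other focal neurologic event occurring after discharge from hospital". The mortality aim in Section 2.4 is "The incidence of all-cause and stroke-related mortality after cardiac surgery", with no exposure named.

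In Section 7.1.1 the Cox model is "used to model time to first atrial fibrillation occurrence and time to first stroke or other focal neurologic event, after discharge from hospital", so post-discharge AF is an outcome there, as it is in the Andersen-Gill and PWP models. On covariates, "The potential risk factors included will be selected based on their univariate association with first event status", along with clinical significance. In Section 7.1.2, "Logistic regression will be used to model the incidence of all-cause" and stroke-related mortality, again with no AF exposure named.

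Section 12.2 lists Figure 3 (stroke) and Figure 4 (mortality), each a time course stratified by whether post-discharge AF occurred. No method is given for either.

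**The concern.** A reader of Sections 1.1 and 2 expects an estimate of how stroke and other adverse events relate to AF arising after discharge. Section 1.2 motivates this with associations from earlier studies that it describes as not risk-adjusted, so an adjusted estimate would be the natural contribution. The analysis section instead treats AF, stroke and death as parallel outcomes of risk factors.

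The comparison survives only in Figures 3 and 4, where the grouping variable is an event that happens during follow-up. A patient must remain alive, and under some codings stroke-free, long enough to enter the AF group. If the curves start at discharge and patients are split by ever/never AF, that guaranteed event-free time is credited to AF. A harmful association could then look absent, and no association could look protective, in the only display that addresses this part of the purpose.

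**Working it through.** **1. Where post-discharge AF appears in the plan**

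| Place | Role of AF |
|---|---|
| 1.1 and 2 | Consequences of AF are part of the purpose |
| 2.3, both primary aims | Preoperative AF is the main risk factor |
| 2.4, aim 3 | Mortality incidence only |
| 7.1.1 Cox, Andersen-Gill, PWP | Post-discharge AF is an outcome; time-dependent terms serve only the proportional-hazards check |
| 7.1.2 Poisson, logistic | No AF exposure named |
| 7.4.3 subgroups | Prior AF and AF at discharge |
| 3.4 and 7.6 | Negative-control analysis is about prior AF |
| 12.1, Tables 3 to 5 | Time-adjusted risks, exposure not named |
| 12.2, Figures 3 and 4 | Curves stratified by post-discharge AF, no method |

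**2. The plan's own power figure (Section 4)**

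Inputs: 4,000 with prior AF, 46,000 without, two-sided 0.05, 80% power.

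h = (1.960 + 0.842) × √(1/4,000 + 1/46,000) = 2.802 × 0.01648 = 0.0462.

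From 25%, h = 0.046 corresponds to 27.0%, a difference of 2.0 points. The stated 0.046 and 2% reproduce. They cover prior AF as exposure and postoperative AF as outcome. No figure exists for post-discharge AF as exposure.

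**3. Size of the bias from ever/never grouping**

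The documents give no annual rates for AF, stroke or death, so these are assumptions: AF 6%, stroke 1.2% and death 4% a year; constant hazards; AF and event times independent under the null; follow-up uniform on 1 to 6 years (surgery 2012 to 2016, follow-up to the end of 2017).

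- Ever/never ratio = (events ÷ total follow-up in AF patients) ÷ (the same in non-AF patients), with all follow-up counted from discharge.
- Time-updated ratio = (events after AF ÷ person-time after AF) ÷ (events before or without AF ÷ person-time before or without AF).

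| Outcome and coding | True 1.0 | True 2.0 |
|---|---|---|
| Stroke, only AF before the stroke counts | about 0.46 | about 0.93 |
| Stroke, any AF in follow-up counts | about 0.99 | about 1.5 |
| Stroke, time-updated AF | about 1.0 | about 2.0 |
| Death, ever/never AF | about 0.47 | – |
| Death, time-updated AF | about 1.0 | – |

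If an ever/never AF indicator were entered in a logistic model of death, the type named in Section 7.1.2, the null odds ratio would be about 0.55.

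Varying the assumptions (three-year AF 3% to 25%, three-year event 5% to 25%), ever/never grouping with AF counted only before the event gives a null rate ratio of 0.44 to 0.51. Time-updated AF gives 0.98 to 1.04.

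**4. What a time-dependent stroke model could detect**

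Minimum HR at 80% power = exp(2.80 ÷ √(D × p × (1 − p))), where D is the number of strokes and p the AF-exposed share. Both are assumed, with N = 50,000.

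- D = 500 (1%), p = 0.03: HR 2.08
- D = 1,000 (2%), p = 0.10: exp(2.80 ÷ √90) = HR 1.34
- D = 2,500 (5%), p = 0.25: HR 1.14

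**The case against.** The strongest reply is that the numbered aims govern, and none asks for the effect of post-discharge AF. Section 2.1 restates the scope as risk factors and incidence. Incidence, risk factors and the prior-AF association are all served by the planned models. On this view the fault lies in the introductory wording, and rewording would cure it. That stands as an alternative remedy. It does not dispose of the point, because Figures 3 and 4 show that the comparison is still intended.

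A reader might go further and infer that the study cannot estimate these consequences. The documents do not support that. Section 7.1.1 already needs dated first AF and first stroke, which is what a time-dependent stroke model requires, and step 4 suggests useful power unless stroke and exposure are both rare.

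A reader might also infer that Sections 7.1.1 and 7.1.2 force AF in as a fixed indicator. They do not. Covariate selection is open-ended, and Cox and Andersen-Gill models accept time-varying covariates. Post-discharge AF is unspecified, neither excluded nor fixed. The logistic model of death is the exception, since it has no way to represent when AF began.

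Finally, the stroke bias is not uniform. If any AF in follow-up counts, including AF after the stroke, there is essentially no bias under the null, only attenuation of a real effect. The documents specify neither coding.

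**Conclusion.** The point holds as a gap in specification: part of the stated purpose has no aim and no adjusted model, and the one planned comparison has no time rule. It should be corrected, and doing so is cheap.

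For death, ever/never grouping from discharge would make no effect look like roughly a halving of the rate (0.47). For stroke, the result could range from making a true doubling look like nothing (0.93) to attenuating it to about 1.5, depending on coding. These sizes rest on assumed rates, constant hazards and independent event times. They show direction and rough size for a grouping that the plan leaves open, and do not predict what the sponsor will report.

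It would be tempting to add that the dates needed are already in hand. For stroke that is reasonable. For death it is not secure: the only death date listed is the surgical-program field MtDate (Appendix 9), Table 1 sources mortality out to five years from the programs, the CHIA minimum merge fields (Appendix 10) include no death date, and Section 8.1 says the final data set holds no CHIA case mix fields.

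**What to change.** 1. Section 7.1.1: add an adjusted Cox model for first stroke or other focal neurologic event with post-discharge AF as a time-dependent covariate, 0 until the date of first post-discharge AF and 1 afterwards. Use the same baseline covariates, including prior AF, and report the hazard ratio with 95% CI as the estimate for this part of the purpose. State in advance how AF first coded during the stroke admission itself is classified.
2. Section 7.1.2: add the matching Cox model for all-cause death, subject to confirming that post-discharge death dates are complete.
3. Section 12.2: draw Figures 3 and 4 with AF status updated over time, or from a landmark day fixed in advance among patients still at risk on that day.
4. If the sponsor does not want this estimate, narrow the purpose in Sections 1.1 and 2 to match the aims and drop the AF stratification from Figures 3 and 4.

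Cost: SAP wording, two more models and a check on death dates. The estimate stays observational, so confounding of AF with stroke and death remains.
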